4.13 Deviations from SAP

Any deviations from the statistical analysis plan will be described and justified in the final Clinical Study Report (CSR).

4.14 Changes in Conduct or Planned Analyses from the Protocol

The statistical analysis for the original protocol and the Extension Period amendment are described in the one SAP to be on hand and not in two different statistical analysis plans.

The data from Treatment Period 1, Treatment Period 2, and Extension Period will be analyzed and presented jointly. Data collected from subjects who are enrolled in the Extension Period will be analyzed together with the data of subjects who are not participating in the Extension Period.

Because of the assumption that a minority (e.g., less than 20%) of subjects will undergo a CSL830 dose increase during the study, the first and second approaches as specified in 11.3.3 of the protocol will not be performed for the secondary safety endpoints. Rather, the approach to safety analysis based upon the actual treatment (40 IU/kg CSL830, 60 IU/kg CSL830 and ≥ 40 IU/kg CSL830) at the time of the event will be performed for the safety analyses.

The analyses by subjects who are randomized to 40 IU/kg CSL830 and who have 1 dose increase; by subjects who are randomized to 40 IU/kg CSL830 and who have 2 dose increases; by subjects who are randomized to 60 IU/kg CSL830 and who have 1 dose increase will not be done.

A treatment group ≥ 40 IU/kg CSL830 has been added in the analyses by treatment and overall group has been deleted.

If an event or evaluation occurred while a subject was receiving 80 IU/kg, these data will be listed and summarized in the ≥ 40 IU/kg CSL830 treatment group.

Adverse events that occur during the Screening will not be summarized for subjects in the Safety Population and will only be listed.

Safety and some efficacy analyses will not be performed for age group. No subgroups of subjects who previously used intravenously administered C1-INH for routine (long-term) prophylaxis will be assessed.

The additional calculation of the primary safety endpoint to divide the number of experienced safety events of the correspondent primary endpoint safety event from all subjects during the treatment duration with the CSL830 dose by the sum of each subject's time at risk in the same CSL830 dose was added and the analyses of the primary safety endpoint will also be performed by actual treatment. Subjects accrue events by dose over the duration(s) they receive each treatment dose while participating in the study, e.g. a subject randomized to 40 IU/kg and up-titrated to 60 IU/kg will be displayed in both treatments as well as in the ≥ 40 IU/kg treatment based upon their corresponding duration in that treatment.

CCI

The evaluation period for efficacy assessments was modified to be from the start (Day 1) of Week 3 of a treatment in Treatment Period 1 until the End of Study Visit (Week 53 Visit) or the last administration of CSL830 + 4 days (whichever occurs first) for subjects who are not participating in the Extension Period. For subjects who are taking part in the Extension Period, the evaluation period will be from the start (Day 1) of Week 3 of the treatment in Treatment Period 1 until the End of Study Visit of the Extension Period (Week 88) or the last administration of CSL830 + 4 days (whichever occurs first).

The analyses of merged HAE attacks (please see for details [Section 4.6](#)) were added as the primary analysis approach. The analyses of the HAE attacks reported by the investigator in the eCRF are kept as secondary analysis approach.

HAE attacks which start between the End of Study Visit or 4th day post last IMP administration [whichever occurs first] and the Follow-up Visit of Treatment Period 2 (applicable for subjects not participating in the Extension Period) or the Extension Follow-up Visit (applicable for subjects participating in the Extension Period) will not be included in the analyses of the secondary efficacy endpoints. For subjects who are taking part in the Extension Period and who have a rest period, HAE attacks with a start date in the rest period will also not be included in the analyses. CCI

The within-subject analyses of subjects who are responders or non-responders before and after a dose increase were deleted.

Different analyses of treated HAE attacks (for details see [Section 4.9.3](#)) have been added. The rescue medications which are included in the calculation of the time-normalized number of uses of rescue medication have been changed to include rescue medications and concomitant medications entered by the investigator in the eCRF which are administered during a merged HAE attack. As a sensitivity analysis, the analyses will be repeated including only rescue medications and concomitant medications which have a date of administration identical to the start date of a merged HAE attack.

The Screening Population was deleted.

CCI

Various subgroup analyses have been added for the efficacy and safety endpoints.

5 Tables and Listings

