2.1.2 Primary Endpoints

The primary endpoints are the person-time incidence rates of each of the following:

- Adverse events leading to premature study discontinuation.
- Thromboembolic events.
- Anaphylaxis.
- HAE attacks resulting in in-patient hospitalization (where hospitalization is the consequence of the need for emergent medical care).
- Solicited AEs (injection site reactions at the CSL830 injection site) graded as severe by the investigator.
- Related serious adverse events (SAEs), other than events specified above.
- Anti-C1-INH antibodies (inhibitory or non-inhibitory).

The person-time incidence rates are the number of subjects experiencing each primary endpoint safety event during treatment with CSL830, divided by the sum of each subject's time at risk.

The primary endpoints will be assessed for Treatment Period 1, Treatment Period 2 and Treatment Periods 1 and 2 (together). The primary endpoints will also be assessed for the Extension Period (only) and for the treatment periods overall for subjects who are included in the Extension Period.

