A descriptive subgroup analysis will be done for subjects who use oral agents for the treatment of HAE and for subjects who do not. A descriptive subgroup analysis will be done for subjects who previously used intravenously administered C1-INH for routine (long-term) prophylaxis. Additional subgroup analyses will be conducted for subjects who participated in study CSL830_3001 and for subjects who did not AND for subjects who are aged < 18 years and ≥ 18 years. Subjects who use oral agents for the treatment of HAE will be flagged in the listings.

Extension Period

Data collected from subjects in the Extension Period will be summarized as follows:

- For the Extension Period only (separate from data collected during Treatment Period 1 and Treatment Period 2)
- For Treatment Period 1, Treatment Period 2 and the Extension Period (combined)

Only data collected from subjects who are enrolled in the Extension Period will be included in these analyses.

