11.3.3.1 Primary Safety Analysis

The person-time incidence rate of each primary endpoint safety event will be assessed as defined above in [Section 11.3.3](#) and overall. The person-time incidence rates are the number of subjects experiencing each primary endpoint safety event during the respective treatment duration with CSL830, divided by the sum of each subject's time at risk in the respective treatment. The person-time incidence rate of each primary endpoint safety event will be assessed for Treatment Period 1 and for the Treatment Periods 1 and 2 overall. For the subjects who are in the Extension Period, the person-time incidence rate of each primary endpoint safety event will also be assessed for the Extension Period and for the treatment periods overall.

Adverse events will be classified using the Medical Dictionary for Regulatory Activities (MedDRA).

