2.1 Primary endpoints

The primary endpoints are the person-time incidence rates of each of the following:

- Adverse events (AEs) leading to premature study discontinuation.
- Thromboembolic events (TEEs).
- Anaphylaxis.
- HAE attacks resulting in in-patient hospitalization.
- Solicited AEs (injection site reactions at the CSL830 injection site) graded as severe by the investigator.
- Related serious AEs (SAEs), other than events specified above.
- Anti-C1-esterase inhibitor (C1-INH) antibodies (inhibitory or non-inhibitory).

For each primary endpoint safety event, the person-time incidence rates are calculated as:

- the number of subjects experiencing the primary endpoint safety event at least once during treatment with CSL830, divided by the sum of each subject's time at risk

and

- the total number of the primary endpoint safety events divided by the sum of each subject's time at risk.

Further details how the number of subjects experiencing the primary endpoint safety event, the number of the primary endpoint safety events and the time at risk will be calculated are outlined in [Section 4.7.1](#).

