4.1 Planned Analyses

The data from Treatment Period 1, Treatment Period 2, and Extension Period will be analyzed and presented jointly, unless specified otherwise.

For subjects who are not participating in the Extension Period, the End of Study Visit will be at Week 53. For subjects who are participating in the Extension Period, the End of Study Visit will be at Week 88.

All summary tables will be presented by treatment groups 40 IU/kg CSL830, 60 IU/kg CSL830, and ≥ 40 IU/kg CSL830 unless specified differently. Events occurring under 80 IU/kg will be summarized in the ≥ 40 IU/kg CSL830 treatment group and otherwise listed only.

Subject disposition will be summarized for all subjects who provide informed consent/assent (as appropriate). Demographic and subject characteristics will be summarized using the ITT and Safety Populations.

All safety data will be summarized using the Safety Population. The analysis of the safety endpoints will be by actual CSL830 treatment (40 IU/kg CSL830, 60 IU/kg CSL830, or ≥ 40 IU/kg CSL830) the subject was taking when the event occurred, unless specified otherwise. In the analysis as treated, a subject contributes events or assessments to each treatment received, e.g. a subject randomized and treated with 40 IU/kg and up-titrated and treated with 60 IU/kg will be displayed in both treatments as well as displayed once in the ≥ 40 IU/kg treatment.

The efficacy endpoints considered as secondary will be summarized using the ITT and PP Populations. CCI

CCI

CCI

Continuous variables will be described by using the mean value with the respective 95% confidence intervals (CI) [only for efficacy variables]; standard deviation; range; 25th, 50th (median), and 75th percentiles; and counts of missing and non-missing values. The geometric coefficient of variation will be expressed as a percentage and the geometric mean and respective 90% CI will be calculated for CCI. The 90% CI for the geometric mean will be calculated by log transforming the data, calculating the lower and upper limits of the 90% CI of the mean of the log-transformed data and, subsequent back transforming the lower and upper limits. Categorical values will be described using counts and percentages. Time variables will be described by median, minimum and maximum and if applicable in addition by mean, standard deviation, 25th and 75th percentiles and graphically represented by Kaplan-Meier curves with the respective 95% CI.

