4.7.1 Primary Safety Analysis

Primary safety endpoints are listed in [Section 2.1](#).

The date of study completion is defined for the safety analyses as the (latest) Follow-up Visit. If a subject discontinued from the study, the date the subject came back to site for a final

study visit will be entered as the date of study discontinuation (to be entered as Week 53 Visit for subjects not taking part in the Extension Period and to be entered as Week 88 Visit for subjects taking part in the Extension Period) or if no further study visit takes place, the date when the subject informed the investigator. The study completion or study discontinuation (whichever applies for the individual subject) is considered as the end of treatment date.

The person-time incidence rates will be calculated in two different ways:

- For the number of subjects experiencing a particular event (bullet points i. below),
- For the number of experienced events (bullet points ii. below).

These 2 analyses approaches for the primary safety endpoints are conducted using 3 different approaches for the selection of the treatment groups which are included in the respective analyses. The following treatment groups will be regarded:

- 1) Treatment, as treated, up until CSL830 dose increase, or either CSL830 discontinuation or study completion – whichever comes first.
- 2) Treatment, as treated at the time of randomization, up to CSL830 discontinuation or study completion – whichever comes first.
- 3) Actual treatment.

In total, six analyses will result and the person-time incidence rates will be calculated

for 1) as

- i. the number of subjects experiencing a given primary endpoint safety event during the treatment duration with CSL830 up until the time of CSL830 dose increase or either CSL830 discontinuation or study completion (whichever is first), divided by the sum of each subject's time at risk. The "time at risk" (in years) is calculated per subject as:

(Date the subject experiences the first event or a CSL830 dose increase or either CSL830 discontinuation or study completion (whichever is first) – date of the subject's first injection of CSL830 in treatment + 1) / 365.25.

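### The SAP pools Treatment Periods 1 and 2 with the Extension without giving a reason, and defines none of the period-specific primary safety rates that the protocol requires

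*SAP*

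**What the plan says.** Protocol 2.1.2 sets the windows for the main study: "The primary endpoints will be assessed for Treatment Period 1, Treatment Period 2 and Treatment Periods 1 and 2 (together". It adds the Extension alone, and all treatment periods in subjects who enter the Extension. Protocol 11.3.3.1 repeats these windows except Treatment Period 2 (TP2) alone; for the main study it says the rates "will be assessed for Treatment Period 1 and for the Treatment Periods 1 and 2 overall". For the Extension summaries, Protocol 11.3.3 states: "Only data collected from subjects who are enrolled in the Extension Period will be included in these analyses".

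SAP 4.1 takes the opposite default: "The data from Treatment Period 1, Treatment Period 2, and Extension Period will be analyzed and presented jointly, unless specified otherwise". SAP 4.14 lists this as a change from the protocol and adds that Extension subjects' data "will be analyzed together with the data of subjects who are not participating in the Extension Period".

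SAP 4.7.1 crosses two numerators (subjects with an event, number of events) with three ways of attributing dose: "In total, six analyses will result and the person-time incidence rates will be calculated". Follow-up runs to the end of the study: "The date of study completion is defined for the safety analyses as the (latest) Follow-up Visit". The seven primary events are kept, and so is the protocol's subject-based numerator: "the number of subjects experiencing the primary endpoint safety event at least once during treatment with CSL830".

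**The concern.** The windows stand in the protocol's primary endpoint section, so they are part of what the primary analysis must deliver. A programmer who follows SAP 4.7.1 exactly would produce whole-study rates and none of the five windowed ones.

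This matters because the primary objective is long-term safety. A single rate over all follow-up is the same whether events cluster early, cluster late or are spread evenly. The late person-time also comes from a selected group: Protocol 11.1 admits to the Extension only US subjects who completed TP2. The pooled denominator therefore mixes the first year of all subjects with later time from a subset.

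**Working it through.** **Text check**

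| Window | Protocol 2.1.2 | Protocol 11.3.3.1 | SAP 4.7.1 |
|---|---|---|---|
| TP1 | yes | yes | no |
| TP2 | yes | no | no |
| TP1+2 | yes | yes | no |
| Extension only | yes | yes | no |
| All periods, Extension subjects | yes | yes | no |

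Every SAP 4.7.1 rate starts at the first injection (of the study, or of a given dose). It ends at the first event (subject-based rates only), a dose increase (two of the three attributions), discontinuation or study completion. None is cut at Week 25, Week 53 or Extension entry, and none is limited to Extension subjects. The primary-endpoint subgroups in SAP 4.7 are oral prophylaxis and roll-over class. SAP 4.7 assigns events after Week 53 to TP2, but no rate uses that assignment. The only reason near the pooling statement in SAP 4.14 (few dose increases expected) explains a different change, to the secondary safety endpoints.

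**The plan's own figure**

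Protocol 11.1 and SAP 3.8 link 100 subjects to an event probability of 3% at 95% confidence. 1 − 0.97^100 = 0.952, so this reproduces. It says nothing about windows.

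**Planned person-years (PY)**

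Inputs are about 110 randomized, 100 completers and about 50 entering the Extension (Protocol 3.5), with visit days from the schedules. I assume 10 withdrawals spread evenly over 367 days: 4.58 in TP1 and 5.42 in TP2. TP1 is taken as 168 days and TP2 as 199. The 50 subjects not entering the Extension add 14 days of follow-up.

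- TP1: (100×168 + 5.42×168 + 4.58×84)/365.25 = 49.5
- TP2: (100×199 + 5.42×99.5 + 50×14)/365.25 = 57.9
- TP1+2: 107.4
- Extension, if all 50 stay to the end: 50×(617+14)/365.25 = 86.4

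Write s for the Extension share of pooled person-time and r for the Extension rate divided by the TP1+2 rate. For event counts, pooled rate ÷ TP1+2 rate = 1 − s + s·r.

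| Extension scenario (assumed) | Extension PY | s | Ratio, r = 0 | Ratio, r = 2 |
|---|---|---|---|---|
| 40 enter, half the time (308.5 days) | 33.8 | 0.24 | 0.76 | 1.24 |
| 50 enter, about 10 months each | 42–44 | 0.28–0.29 | 0.71–0.72 | 1.28–1.29 |
| 50 enter, full 88 weeks plus follow-up | 86.4 | 0.45 | 0.55 | 1.45 |
| 60 enter, full 88 weeks plus follow-up | 103.7 | 0.49 | 0.51 | 1.49 |

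The second row rests on an inference. SAP 4.6.3.1 stops its cumulative windows at 22 months, although 52 + 88 weeks is about 32 months. Protocol 3.3 also refers to a study end date that can shorten late entrants' Extension.

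The formula is only approximate for the subject-based rate, where time stops at the first event. With a constant rate of 2 per 100 PY in TP1+2 and the third scenario, the ratios are 0.56 (r = 0) and 1.43 (r = 2).

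**What pooling hides (third scenario, total 193.8 PY)**

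Ten events give 10/193.8 = 5.2 per 100 PY (95% CI 2.5 to 9.5 by the SAP formula) in each of these cases:

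- 10 and 0 events in TP1+2 and the Extension: 9.3 and 0 per 100 PY
- 6 and 4 events: 5.6 and 4.6 per 100 PY
- 2 and 8 events: 1.9 and 9.3 per 100 PY

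**The case against.** Several points on the other side stand.

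- The pooling is disclosed in the SAP section meant for changes from the protocol. A reader might infer that it was concealed; the documents do not support that. What is missing is the reason and the rates.
- SAP 4.1 allows exceptions, and the table shells and interim SAPs are separate documents that we did not have. A reader might infer that windowed rates will never be reported. The documents support only that no available SAP text defines them. The SAP does set time windows for the responder endpoint, so it can specify them when intended.
- A reader might infer that the SAP shows nothing about change over time. That goes too far. Antibody status is summarized by visit (SAP 4.7.2.3), DVT and PE risk scores are summarized by visit (SAP 4.7.5), and listings are planned. These partly show change over time, but they are not person-time rates.
- Person-time methods already allow for unequal follow-up, as SAP 4.12 says. They do so for duration, but cannot reveal a rate that varies over time.
- The analysis is descriptive, and windowed rates will be imprecise. That is a cost of the fix and does not explain why the windows were dropped.

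**Conclusion.** The point holds and should be fixed. The SAP replaces the protocol's windowed primary safety rates with pooled ones, gives no reason, and defines none of the five windows in SAP 4.7.1. Four of the five appear in both protocol sections; TP2 alone appears in 2.1.2 but not in 11.3.3.1, so the protocol must be reconciled there.

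The size is illustrative. With an Extension share of 24% to 49%, the pooled event-count rate is roughly 0.51 to 0.76 times the TP1+2 rate if the Extension rate is zero, and 1.24 to 1.49 times if it is double. The share depends on how many subjects enter the Extension and how long they stay. A reader might take the 45% full-follow-up figure as the expected one; the study end date rule and the 22-month windows make it too firm. A reader might also infer that the pooled rates are biased. The documents do not show that: any difference between periods is of unknown size and direction.

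**What to change.** In SAP 4.7.1, keep the joint rates and add the following, with the existing chi-square interval:

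- **Windows.** TP1, TP2 (once Protocol 2.1.2 and 11.3.3.1 are reconciled) and TP1+2 in all Safety Population subjects; Extension only and all periods in Extension enrollees.
- **Dose attribution.** Use Protocol 11.3.3: randomized group up to the first dose increase, and randomized group regardless of increase. Add the combined ≥40 IU/kg group. The actual-treatment attribution, which the SAP added, may be shown as well but does not replace these.
- **Boundaries.** Use the same cut dates for events and person-time, following the SAP 4.7 assignment rule. State whether rest time counts: SAP 4.4.1 leaves it out of exposure, while SAP 4.7.1 does not subtract it from time at risk.
- **Antibodies.** Protocol 3.1.2 ends TP1 with the Week 25 Visit, but SAP 3.1.3 excludes that visit. Reconcile them so that the Week 25 sample falls in TP1. In the main study, samples are scheduled only at Day 1, Week 25 and Week 53, so TP1 would otherwise have no scheduled post-baseline sample. Count only subjects newly positive in the window, and remove those already positive at its start. Protocol 1.4 notes that such antibodies occur regardless of C1-INH exposure.

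If pooling alone is intended, give the reason in SAP 4.14.

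The cost is SAP text and reruns of an existing formula on dates already collected. With two arms under two attributions plus the combined group (5 columns), 7 events × 5 windows × 5 columns = 175 subject-based rates, or 350 with both numerators. The plan already has 7 × 6 × 3 = 126. Intervals will be wide. The upper 95% limit with zero events is 3.689/PY: 7.4 per 100 PY for TP1 (14.9 per arm), 6.4 for TP2, 3.4 for TP1+2 and, with full follow-up, 4.3 for the Extension, against 1.9 pooled.

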3.5 Planned Number of Subjects

The study plans to enroll subjects who complete participation in CSL830_3001. Additional subjects who have not participated in study CSL830_3001 will be enrolled so that the total number of subjects randomized is approximately 110.

Assuming that up to 10% of subjects withdraw before the completion of the study, 100 subjects are planned to complete the study.

Subjects from the United States who have completed Treatment Period 1 and Treatment Period 2 according to the study protocol are eligible to enroll in the Extension Period. Approximately 50 of these subjects are anticipated to enroll in the Extension Period.

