11.3.3 Safety Analyses

The Safety Population will be used for analyses of safety.

Treatment Period 1 and Treatment Period 2

All subjects in the Safety Population will be included in the safety analyses. The primary safety analysis will be performed by treatment group (ie, subjects who are randomized to 40 IU/kg CSL830 and by subjects who are randomized to 60 IU/kg CSL830). Data collected from those subjects will be included in the 40 IU/kg and 60 IU/kg CSL830 treatment groups, respectively, until the time they undergo the final study visit or they undergo a CSL830 dose increase, whichever comes first.

A secondary safety analysis will be performed by treatment group [ie, subjects who are randomized to 40 IU/kg CSL830 and by subjects who are randomized to 60 IU/kg CSL380, regardless of any dose increase(s)]. Data collected from those subjects will be included in the

40IU/kg and 60IU/kg CSL830 treatment groups, respectively, until the time they undergo the final study visit.

The analyses will be done both for Treatment Period 1 (only) and for Treatment Period 1 and 2 (together), unless otherwise noted.

Furthermore, safety analyses will be summarized by subjects who are randomized to 40 IU/kg CSL830 and who have 1 dose increase; by subjects who are randomized to 40 IU/kg CSL830 and who have 2 dose increases; by subjects who are randomized to 60 IU/kg CSL830 and who have 1 dose increase.

After the dose increase, data collected from subjects who undergo a 20 IU/kg dose increase from 40 IU/kg to 60 IU/kg or from 60 IU/kg to 80 IU/kg in Treatment Period 1 will be summarized separately for the 60 IU/kg and 80 IU/kg CSL830 doses. Furthermore, data collected from subjects who undergo a 20 IU/kg dose increase from 40 IU/kg to 60 IU/kg or from 60 IU/kg to 80 IU/kg in Treatment Period 2 will also be summarized separately for the 60 IU/kg and 80 IU/kg CSL830 doses.

After a second dose increase, data collected from subjects who undergo a 20 IU/kg x 2 dose increase from 60 IU/kg to 80 IU/kg in Treatment Period 1 will be summarized separately for the 80 IU/kg CSL830 dose. Furthermore, data collected from subjects undergo a 20 IU/kg x 2 dose increase from 60 IU/kg to 80 IU/kg in Treatment Period 2 will also be summarized separately for the 80 IU/kg CSL830 dose.

Subjects who undergo a CSL830 dose increase will be flagged in the listing

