3.6 Randomization

A block randomization with 1:1:1-stratification for “CSL830-Continuation” Subjects, “CSL830-Interrupted” Subjects, and “CSL830- Naïve” Subjects will be used to ensure that subjects are randomized in balanced manner to a starting dose of CSL830 of either 40 IU/kg or 60 IU/kg.

Eligible subjects will be randomized to 1 of the 2 treatment groups (CSL830 40 IU/kg or CSL830 60 IU/kg) by means of Interactive Response Technology (IRT) according to the above mentioned randomization scheme. The IRT will assign the appropriate study treatment to each subject.

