3.8 Sample Size

100 subjects are planned to complete the study. The sample size is based on guidelines issued by the International Conference on Harmonisation, ICH 1994 [1] and not on statistical calculations. The sample size of 100 subjects allows observation of ≥ 1 adverse event with a probability of 3% at 95% confidence.

4 Statistical Methodology

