4.7.2 Safety Analysis of the Secondary Safety Endpoints

Secondary safety endpoints are listed in [Section 2.2.1](#).

Adverse event data will be presented in individual listings and summary tables.

The analysis of the secondary safety endpoints will be by actual CSL830 treatment (40 IU/kg or 60 IU/kg and ≥ 40 IU/kg) the subject was taking when the event occurred. In this analysis, a subject contributes events in each treatment received, e.g. a subject randomized and treated with 40 IU/kg and up-titrated and treated with 60 IU/kg will be displayed in both treatments as well as displayed once in the ≥ 40 IU/kg treatment.

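### Secondary safety endpoints that are not also primary are tabulated only by dose at the time of the event, so they have no summary table by starting dose

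*SAP*

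**What the plan says.** Protocol 11.3.3 groups safety data by randomized dose in two ways. The first (approach 1) includes a subject's data "until the time they undergo the final study visit or they undergo a CSL830 dose increase, whichever comes first". The second (approach 2) follows the randomized groups to the final visit whatever dose increases occur. Protocol 11.3.3.2 refers back to these groupings for the secondary safety summaries.

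SAP 4.14, which lists changes from the protocol, states that "the first and second approaches as specified in 11.3.3 of the protocol will not be performed for the secondary safety endpoints". The reason given is an assumption that only a minority, for example under 20%, will have a dose increase. SAP 4.7.2 then tabulates by the dose being taken when the event occurred, so that "a subject randomized and treated with 40 IU/kg and up-titrated and treated with 60 IU/kg will be displayed in both treatments", and once more in the combined column for 40 IU/kg and above. SAP 4.3 assigns Safety Population members to every dose they received. SAP 4.1 places events under 80 IU/kg in the combined column and otherwise only lists them.

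SAP 4.7.1 differs for the primary safety endpoints. It keeps three groupings: up to dose increase, by treatment at the time of randomization regardless of increases, and by actual dose.

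**The concern.** Subjects are "randomized in balanced manner to a starting dose of CSL830 of either 40 IU/kg or 60 IU/kg", and readers will compare the adjacent 40 and 60 IU/kg columns whether or not a test is planned. In actual-dose tables those columns are not the randomized groups. Eligibility for an increase depends on attack frequency and the decision is the investigator's, so subjects entering the 60 IU/kg column late are selected. Each counts as a full subject in both denominators while their observation time is split between them.

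The stated reason does not support the deletion. If few subjects escalate, starting-dose tables add little burden and nearly agree with the actual-dose tables; if many escalate, they are needed. At stake is whether a dose difference, or the lack of one, in the general AE tables can be read as an effect of starting dose.

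**Working it through.** **The plan's own figure.** SAP 3.8 says: "The sample size of 100 subjects allows observation of ≥ 1 adverse event with a probability of 3% at 95% confidence". Check: 1 - 0.97^100 = 95.2%, and the rate detectable with 95% probability is 1 - 0.05^(1/100) = 2.95%. The figure reproduces and is not in dispute. It implies no power for comparing doses.

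**Inputs from the documents.** Protocol 3.5: "the total number of subjects randomized is approximately 110", taken here as 55 per arm. SAP 4.14: escalation assumed below 20%. Protocol 3.2: the lower attack threshold for an increase applies from the Week 25 Visit.

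**Assumptions not in the documents.** Only the 40 IU/kg arm escalates, by one step; AE risk is equal at both doses; follow-up is 52 weeks. The first-AE hazard is either front-loaded (2.0/yr for 13 weeks, then 0.3/yr) or constant (1.0/yr).

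**Overlap.** At 20%, 0.20 × 55 = 11 subjects are in both columns. The 60 IU/kg column has 66 subjects, 11/66 = 16.7% of them not randomized to 60, and the two columns sum to 121 for 110 randomized. With a step-up after 24 weeks these subjects supply 11 × 28 / (55 × 52 + 11 × 28) = 308/3168 = 9.7% of that column's person-time.

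**Crude percentages.** Let H(t) be cumulative hazard, e the share escalating and t the time of escalation.
- 40 column = (1 - e)[1 - exp(-H(52))] + e[1 - exp(-H(t))]
- 60 column = {[1 - exp(-H(52))] + e[1 - exp(-(H(52) - H(t)))]} / (1 + e)

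Worked case, front-loaded, e = 0.20, t = Week 33:
- H(52) = 2.0 × 0.25 + 0.3 × 0.75 = 0.725, so each randomized arm has 51.57%.
- H(33) = 0.5 + 0.3 × (33/52 - 0.25) = 0.615, giving 45.96%; the remaining 0.110 gives 10.38%.
- 40 column: 0.8 × 51.57 + 0.2 × 45.96 = 50.4%.
- 60 column: (51.57 + 0.2 × 10.38)/1.2 = 44.7%.
- False difference: -5.7 points.

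False 60-minus-40 difference, in points:

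| Hazard | Share escalating | Week 25 | Week 33 | Week 41 |
|---|---|---|---|---|
| Front-loaded | 10% | -2.6 | -3.2 | -3.8 |
| Front-loaded | 20% | -4.6 | -5.7 | -6.9 |
| Constant | 10% | +0.4 | -1.3 | -3.1 |
| Constant | 20% | +1.2 | -2.2 | -5.6 |

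**Both arms escalating.** With 20% of each arm stepping up at 24 weeks, a constant hazard of 0.3 to 1.0/yr, and the same or doubled hazard in escalators, the false difference is -2.7 to +0.6 points. Both columns also fall below the randomized percentage. At hazard 1.0/yr without doubling they read 58.0% and 55.2% against 63.2%.

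**Events per year.** With a constant rate of 1.0/yr both columns read 1.0, so there is no distortion from exposure length. If the front-loaded curve is read as an event rate, the worked case gives (0.8 × 0.725 + 0.2 × 0.615)/(0.8 + 0.2 × 33/52) = 0.76/yr for 40 and (0.725 + 0.2 × 0.110)/(1 + 0.2 × 19/52) = 0.70/yr for 60, against 0.725 in each randomized arm.

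**Which dropped grouping helps.** Constant hazard, 20% escalating at Week 25: full follow-up gives 63.21%, Week 25 gives 38.17%, and the remaining time gives 40.50%.
- Approach 1: 0.8 × 63.21 + 0.2 × 38.17 = 58.2% against 63.2%, a false +5.0.
- Actual dose: 58.2% against (63.21 + 0.2 × 40.50)/1.2 = 59.4%, a false +1.2.
- Approach 2: 63.2% in both.

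**The case against.** The change is declared and explained in SAP 4.14, no test of 40 against 60 IU/kg on safety is planned, and SAP 3.8 states: "The sample size is based on guidelines issued by the International Conference on Harmonisation, ICH 1994 [1] and not on statistical calculations". That stands: this is a weakness of analysis choice, not a contradiction.

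A reader might infer that the whole 40 versus 60 IU/kg safety picture is no longer randomized, or that every secondary safety endpoint loses its starting-dose view. The documents do not support either. SAP 4.7.1 keeps starting-dose rates with 95% confidence intervals for AEs leading to discontinuation, TEEs, anaphylaxis, HAE hospitalizations, severe solicited AEs, other related SAEs and anti-C1-INH antibodies, and several of these are also secondary endpoints. The by-subject listing of solicited AEs in SAP 4.7.2.1 also shows the randomized dose.

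A reader might also infer that escalators contribute only short, late time at 60 IU/kg. The SAP pools the Extension Period, and an extension subject escalated at Week 33 could have 19 + 88 = 107 weeks at the new dose. The 52-week model does not describe those subjects. Roll-over subjects previously exposed to CSL830 also weaken the front-loaded hazard.

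Finally, SAP 4.7.2.1 provides events per injection and per subject-year. These handle exposure length, but not late entry when risk changes over time, nor selection of who escalates.

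**Conclusion.** The point holds for the secondary safety endpoints that are not also primary: overall AEs, all SAEs, related and temporally-related AEs, suspected ADRs, non-severe solicited AEs, hypersensitivity, DVT/PE risk scores and laboratory summaries. Their actual-dose columns describe events by dose received and do not compare the starting-dose groups.

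The textual finding is firm; its numerical size is not. Within the SAP's escalation ceiling, and under the 52-week, 40-arm-only, equal-risk assumptions, the false difference in crude percentages is about -2.6 to -6.9 points (front-loaded) or +1.2 to -5.6 points (constant). It is smaller if both arms escalate alike, and absent from event rates under a constant hazard. These figures are illustrations and do not predict the trial's tables.

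Restoring only the grouping cut off at dose increase would not settle it. That cut-off is driven by attacks and can distort crude percentages more than actual dose does. Only the grouping regardless of dose increase keeps the starting-dose groups whole; because the Safety Population is analysed as treated, this means the starting dose actually received.

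**What to change.** In SAP 4.7.2 and 4.14, add tables by treatment at the time of randomization regardless of dose increase, as SAP 4.7.1 already defines it, for the AE overview, SAEs, related and temporally-related AEs, and solicited AEs per subject and per injection, with exposure-adjusted rates. Suspected ADRs come with the AE overview. Base any 40 versus 60 IU/kg statement on these tables. The grouping cut off at dose increase can be added as supportive. Keep the actual-dose tables as the description by dose received, and label summaries that exist only in that form (hypersensitivity, risk scores, laboratory) accordingly.

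The cost is SAP wording and a few more tables from existing programs, since the treatment variable and dates are already specified. The drawback is that events after escalation are attributed to the starting dose. With 20% escalating at Week 33, 0.20 × 19/52 = 7.3% of the 40 IU/kg group's 52-week person-time would be at 60 IU/kg. That is why the actual-dose tables should stay alongside.
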